10.2.3. Severity of Adverse Events

For both serious and non-serious AEs, the Investigator must determine both the intensity of the event and the relationship of the event to study drug administration. Only those injection site reactions considered clinically significant by the Investigator will be recorded as AEs.

Intensity of all AEs including clinically significant treatment-emergent laboratory abnormalities, injection site reactions, and potential systemic reactions, where appropriate, will be guided per the Common Terminology Criteria for Adverse Events (CTCAE). The CTCAE grade refers to the severity of the AE and ranges from Grade 1 (mild AE), Grade 2 (moderate AE), Grade 3 (severe AE) and Grade 4 (life-threatening or disabling AE) to Grade 5 (death related to AE).

AEs not listed by the CTCAE will be graded as follows:

- **Mild:** discomfort noticed but no disruption of normal daily activity.
- **Moderate:** discomfort sufficient to reduce or affect daily activity.
- **Severe:** inability to work or perform normal daily activity.
- **Life-threatening:** represents an immediate threat to life.

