^b A comprehensive skin evaluation will be performed by the Investigator at Screening. If any concerning lesions are identified during the screening period, the subject should be referred to a dermatologist for assessment and potential biopsy and results should be confirmed as to whether the lesion is benign prior to first dose of setmelanotide. If the pre-treatment biopsy results are of concern, the subject will be excluded from the study.

^c Height will only be collected at Screening.

^d Supine blood pressure, supine heart rate, pulse rate, and tympanic (ear) body temperature. Heart rate and blood pressure will be measured using the same arm for each reading after the subject has been resting in the supine position for at least 5 minutes. For timepoints at which vital signs, PK blood samples, and/or ECGs are all to be collected, ECGs should be collected first followed by vital signs then PK samples, with the timing of the PK sample to occur at the nominal time.

^e Serum pregnancy test will be performed at Screening. Urine pregnancy test will be performed on all other designated days.

^f On the evening before continuous Holter ECG sampling, subjects will undergo a 10-hour overnight fast.

^g Breakfast is to be administered at approximately 7:00 AM every day in the CRU (30 minutes pre-dose). Lunch, dinner, and a snack will be administered at approximately 12:00 PM (after 4-hour assessments), 6:00 PM (after 10-hour assessments), and 9:00 PM, respectively.

^h **Group 1** will receive SC setmelanotide QD (approximately 7:30 AM) at a dose of 2 mg from Days 1 to 7; 3 mg from Days 8 to 10; 5 mg from Days 11 to 13; and 7 mg from Days 14 to 16.

Groups 2 and 3 will receive SC placebo QD (approximately 7:30 AM) from Days 1 through 16.

All doses will be double-blinded.

ⁱ **Group 1** will receive oral placebo with their SC setmelanotide dose on Days 10 and 16.

Group 2 will receive oral moxifloxacin 400 mg on Day 10 and oral placebo on Day 16.

Group 3 will receive oral placebo on Day 10 and moxifloxacin 400 mg on Day 16.

All doses will be double-blinded. On Days 10 and 16, subjects should receive SC setmelanotide/placebo first. Oral moxifloxacin/placebo should then be administered within 2 minutes of the SC dose.

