4.2. Secondary Objectives

The secondary objectives of this study are:

- To assess the effects of therapeutic and supratherapeutic setmelanotide concentrations on HR, PR interval, QRS interval, T-wave morphology, and cardiac safety in healthy subjects.
- To evaluate assay sensitivity and the effect of a positive control, a single 400 mg oral dose of moxifloxacin, on the QT/QTcF interval in healthy subjects.
- To assess the pharmacokinetics (PK) of setmelanotide following administration of therapeutic and supratherapeutic doses of SC setmelanotide in healthy subjects.
- To evaluate the safety and tolerability of therapeutic and supratherapeutic doses of SC setmelanotide in healthy subjects.

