10.2. Adverse Events

10.2.1. Definition of Adverse Events and Serious Adverse Events

10.2.1.1. Adverse Event

An AE is any untoward medical occurrence associated with the use of a drug in humans, whether or not considered drug related. An adverse event (also referred to as an adverse experience) can be any unfavorable and unintended sign (e.g., an abnormal laboratory finding), symptom, or disease temporally associated with the use of a drug, without any judgment about causality. An AE can arise from any use of the drug (e.g., off-label use, use in combination with another drug) and from any route of administration, formulation, or dose, including an overdose.

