10.2.4. Procedures for AE and SAE Reporting

Each subject must be carefully monitored for the development of any AEs. This information should be obtained in the form of non-leading questions (e.g., “How are you feeling?”) and from signs and symptoms detected during each examination, observations of study personnel, and spontaneous reports from subjects.

All AEs (serious and non-serious) spontaneously reported by the subject and/or in response to an open question from study personnel or revealed by observation, physical examination, or other diagnostic procedures will be recorded on the appropriate eCRF. Any clinically relevant deterioration in laboratory assessments or other clinical findings is considered an AE and must be recorded on the appropriate eCRF. When possible, signs and symptoms indicating a common underlying pathology should be noted as one comprehensive event.

All SAEs that occur during the study must be reported by the Investigator to the Medical Monitor within 24 hours from the point in time when the Investigator becomes aware of the SAE. All SAEs must be reported whether or not considered causally related to the study drug. SAE forms will be completed, and the information collected will include subject number, a narrative description of the event, and an assessment by the Investigator as to the severity of the event and relatedness to study drug. Follow-up information on the SAE may be requested by the Sponsor or its designee.

If there are serious, unexpected adverse drug reactions associated with the use of the study drug, the Sponsor or designee will notify the appropriate regulatory agency(ies), Independent Ethic Committees (IECs) and all participating investigators on an expedited basis. It is the responsibility of the Investigator to promptly notify the Institutional Review Board (IRB)/IEC where required by the IRB/IEC of all unexpected serious adverse drug reactions involving risk to human subjects.

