4.11 Safety Evaluation

All safety summaries and analyses will be based upon the Safety Population as defined in Section 4.4 of this document.

All summaries will be provided by treatment group.

Placebo across treatment group will be pooled.

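### Injection-site reactions are recorded as adverse events only if the investigator judges them clinically significant, with no criterion, so the TEAE tables can under-count them for every SC injection by an amount that cannot be estimated

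*Protocol*

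**What the plan says.** Protocol 10.2.3 sets a special recording rule: "Only those injection site reactions considered clinically significant by the Investigator will be recorded as AEs". It does not say what makes a reaction clinically significant, and it makes no distinction by dose or arm.

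Two neighbouring sections are broader. Protocol 10.2.1.1 reads "An AE is any untoward medical occurrence associated with the use of a drug in humans, whether or not considered drug related". Protocol 10.2.4 covers "All AEs (serious and non-serious) spontaneously reported by the subject and/or in response to an open question from study personnel", together with those found by observation, examination or other procedures, and requires them to be recorded on the eCRF.

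Protocol 4.2 lists as a secondary objective "To evaluate the safety and tolerability of therapeutic and supratherapeutic doses of SC setmelanotide in healthy subjects". The matching endpoint in Protocol 5.2.4 and SAP 3.2.4 is the frequency and severity of adverse events.

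On reporting, SAP 4.11 says "All summaries will be provided by treatment group" and "Placebo across treatment group will be pooled". SAP 4.11.1 plans three TEAE tables: by system organ class and preferred term, then adding relationship, then adding severity. It also plans a by-subject listing of all adverse events.

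**The concern.** The product is injected daily for 16 days, and its tolerability is a stated objective measured through adverse events. For this one type of event, an undefined judgement decides whether it enters the adverse-event data at all. A reaction that fails the judgement is not graded and not tabulated. Two investigators, or one investigator on two days, could draw the line differently, and the data would not show it.

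What is at stake is the meaning of the reported injection-site incidence. A reader of the TEAE tables would take it as the rate of reactions, when it is the rate of reactions judged clinically significant. No later analysis could restore events missing from the adverse-event data.

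**Working it through.** The plan states no reaction rate, expected count or precision for this outcome, so there is no figure of its own to reproduce. The main check is a reading of the text.

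**1. The three recording rules side by side (Protocol).**
- 10.2.1.1: any untoward occurrence is an adverse event; no significance threshold.
- 10.2.4: all adverse events, serious or not, however detected, go on the eCRF.
- 10.2.3: injection-site reactions are recorded as adverse events only if judged clinically significant.

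A reaction the subject reports but the investigator considers insignificant is recorded under the first two and not under the third. No section says which prevails.

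**2. Is there another capture route?**
- Comprehensive skin examination: Screening only (Protocol 10.1.3 and Table 1).
- Physical examination: SAP Table 6-1 shows none from Day 1 to Day 16, and SAP 4.11.7 tabulates and lists only clinically significant findings.
- Injection-site scale, diary or separate listing: none in the readable text.
- Laboratory data, for contrast: SAP 4.11.3 also ties adverse-event status to clinical significance, but every laboratory value is still listed, and results are summarised with shift tables for hematology and biochemistry. A filtered injection-site reaction has no such fallback.

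**3. Which outputs are exposed?** All three TEAE tables and the by-subject listing in SAP 4.11.1 draw on recorded adverse events. The listings in SAP 4.11.2 cover serious events, deaths, other significant events and withdrawals. A serious reaction, or one leading to withdrawal, would be expected to pass the filter.

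**4. Illustration only; the rates are assumptions.** With 72 subjects randomised 1:1:1, Group 1 has n = 72 / 3 = 24. Let p be the true proportion of subjects with a reaction and s the share of those subjects who have one judged clinically significant. Expected subjects recorded = 24 × p × s. Chance that at least one is recorded = 1 − (1 − p × s)^24. Each cell gives the expected number recorded and that chance.

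| p (true number) | s = 100% | s = 50% | s = 20% | s = 5% |
|---|---|---|---|---|
| 10% (2.4) | 2.4; 92% | 1.2; 71% | 0.48; 38% | 0.12; 11% |
| 30% (7.2) | 7.2; >99% | 3.6; 98% | 1.44; 77% | 0.36; 30% |
| 50% (12.0) | 12.0; >99% | 6.0; >99% | 2.4; 92% | 0.6; 46% |

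At s = 100% nothing is lost; below that the loss depends wholly on s, about which the documents say nothing.

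**5. Comparison with placebo under an equal filter.** If s is the same in both arms, the risk difference becomes s × (p_T − p_C) and the risk ratio stays p_T / p_C. With assumed 50% against 30%, the difference is 20 points at s = 100%, 10 at 50% and 4 at 20%; the ratio stays 0.50 / 0.30 = 1.67.

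**The case against.** The best defence is that this is an openly stated convention. A specific rule may qualify a general one, and the protocol uses a similar threshold elsewhere: Protocol 10.2.4 refers to clinically relevant deterioration in laboratory and other clinical findings, and Protocol 10.1.2 requires clinically significant examination changes to be recorded. Safety is descriptive, the study exists to answer a QT question, and the investigator and site staff are blinded (Protocol 7.5), so the filter need not favour an arm. Parts of the schedule, the safety endpoints and the SAP around section 4.12 are redacted, so a separate collection of injection-site findings cannot be excluded. The rule also does not forbid notes in source documents.

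Much of this stands, and it limits the point. Blinding protects the contrast but does not restore absolute incidence, and s could still differ between arms if reactions differ in intensity. The convention argument does not supply the missing criterion or a fallback record.

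A reader might go further and infer three things that the documents do not support.
- *That local tolerability of 5 and 7 mg is understated in every adverse-event table.* The rule applies at all four setmelanotide dose levels and to placebo. The tables are by treatment group, so none estimates 5 or 7 mg separately; that is a different gap. The listings in SAP 4.11.2 should be little affected.
- *That exactly the mild reactions are removed.* Grade and clinical significance are different judgements. Protocol 10.2.3 does not equate a non-significant reaction with Grade 1, and its grading sentence says how recorded events are graded, not that all reactions are events.
- *That under-counting is established.* It requires reactions to occur and be judged not significant, and no rate is given for either.

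**Conclusion.** The point holds as a defect of data capture. Protocol 10.2.3 is in conflict with 10.2.1.1 and 10.2.4, leaves the criterion undefined, and in the readable text leaves the remaining reactions uncaptured. The direction is certain: recorded incidence can equal the true incidence or fall below it, never exceed it. The size cannot be estimated from the documents; under the assumed ranges it runs from no loss to nearly all affected subjects missing. The exposure is to the TEAE incidence, relationship and severity tables, for all SC injections. The contrast with placebo is not necessarily biased, and the primary QTc analysis is unaffected. The conclusion rests on there being no separate injection-site collection in the redacted text. It is worth correcting because it bears on a stated secondary objective and is cheap to correct.

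**What to change.** Reconcile Protocol 10.2.3 with 10.2.1.1 and 10.2.4 so that every observed or reported injection-site reaction is entered on the eCRF with its grade and the dose at onset. Keep clinical significance as an additional field, and say what that judgement rests on. In SAP 4.11.1, report all injection-site reactions and, beside them, the clinically significant subset. If a redacted section already provides for this, 10.2.3 should refer to it.

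The cost is protocol and SAP wording and more low-grade eCRF entries. Subjects are confined to the unit through the morning of Day 17 and study staff give the injections, so no extra visit or procedure is needed. No dose or treatment rule changes.

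If the filter is kept, the report must label injection-site incidence as covering clinically significant reactions only.

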10.2.4. Procedures for AE and SAE Reporting

Each subject must be carefully monitored for the development of any AEs. This information should be obtained in the form of non-leading questions (e.g., “How are you feeling?”) and from signs and symptoms detected during each examination, observations of study personnel, and spontaneous reports from subjects.

All AEs (serious and non-serious) spontaneously reported by the subject and/or in response to an open question from study personnel or revealed by observation, physical examination, or other diagnostic procedures will be recorded on the appropriate eCRF. Any clinically relevant deterioration in laboratory assessments or other clinical findings is considered an AE and must be recorded on the appropriate eCRF. When possible, signs and symptoms indicating a common underlying pathology should be noted as one comprehensive event.

All SAEs that occur during the study must be reported by the Investigator to the Medical Monitor within 24 hours from the point in time when the Investigator becomes aware of the SAE. All SAEs must be reported whether or not considered causally related to the study drug. SAE forms will be completed, and the information collected will include subject number, a narrative description of the event, and an assessment by the Investigator as to the severity of the event and relatedness to study drug. Follow-up information on the SAE may be requested by the Sponsor or its designee.

If there are serious, unexpected adverse drug reactions associated with the use of the study drug, the Sponsor or designee will notify the appropriate regulatory agency(ies), Independent Ethic Committees (IECs) and all participating investigators on an expedited basis. It is the responsibility of the Investigator to promptly notify the Institutional Review Board (IRB)/IEC where required by the IRB/IEC of all unexpected serious adverse drug reactions involving risk to human subjects.

10.2.5. Adverse Event Monitoring and Follow-up

Monitoring of AEs will be conducted throughout the study. AEs will be recorded in the eCRFs from Screening through the Follow-up visit. AEs that occur after the start of study drug administration will be considered treatment-emergent adverse events (TEAEs). SAEs will be recorded through the Follow-up visit. All AEs should be monitored until they are resolved.

After the initial AE/SAE report, the Investigator is required to proactively follow each subject at subsequent visits/contacts. All SAEs will be followed until resolution, stabilization, the event is otherwise explained, or the subject is lost to follow-up.

Any SAE that occurs at any time after completion of the study, which the Investigator considers to be related to study drug, must be reported to the Sponsor or designee.

In the event a subject is withdrawn from treatment due to an AE, the subject should be encouraged to complete the final study/early termination visit to monitor the event to resolution and obtain additional protocol defined safety assessments.

10.2.6. Depression or Suicidality

A subject should be referred to an MHP if he/she has:

- Any suicidal behavior.
- Any suicidal ideation of type 4 or 5 on the C-SSRS.

A referral to a MHP should also be made if in the opinion of the Investigator it is necessary for the safety of the subject. If a subject's psychiatric disorder can be adequately treated with psycho- and/or pharmacotherapy, then the subject, at the discretion of the MHP, should be continued in the study.

11. STATISTICS

11.1. Sample Size Determination

11.1.1. Sample Size for Setmelanotide C-QTc Analysis

A sample size of 60 evaluable subjects who complete the study (20 subjects in Group 1 receiving SC setmelanotide and 20 subjects each in Groups 2 and 3 receiving SC placebo) will provide at least 85% power to exclude that setmelanotide causes more than 10 msec QTc effect at clinically relevant plasma levels, as shown by the upper bound of the 2-sided 90% confidence interval (CI) of the model-predicted QTc effect ($\Delta\Delta\text{QTcF}$) at the observed geometric mean Cmax of setmelanotide on Day 10 and Day 16 in the study individually. This power is estimated approximately using a 2-sample t-test using nQuery 8 (www.statsols.com). The calculation assumes a 1-sided 0.05 significance level, a small underlying effect of setmelanotide of 3 msec and a standard deviation (SD) of the ΔQTcF of 8 msec for both SC setmelanotide and SC placebo. Note that this calculation is conservative, since it does not take into account any gain in precision due to the use of all data from each subject with the help of a linear mixed effects model. The concentration-QTc analysis method is supported by [Darpo \(2015\)](#) and [Ferber \(2015\)](#).

11.1.2. Sample Size for Assay Sensitivity of C-QTc Analysis

To demonstrate assay sensitivity with C-QTc analysis, it must be shown that the $\Delta\Delta\text{QTcF}$ of a single dose of 400 mg moxifloxacin exceeds 5 msec (i.e., the lower bound of the 2 sided 90% CI of the predicted QTcF effect [$\Delta\Delta\text{QTcF}$] should exceed 5 msec) at the observed geometric mean Cmax of 400 mg moxifloxacin. Under the assumption that the predicted moxifloxacin QTc effect is 10 msec with a SD of ΔQTcF of 8 msec for both oral moxifloxacin and oral placebo, a sample size of 40 evaluable subjects in a crossover of moxifloxacin and placebo will provide at least 81% power to demonstrate assay sensitivity with a 1-sided 0.05 significant level. The power to detect the effect of moxifloxacin on QTc over the entire crossover period is at least 86%. This power is estimated approximately using a 2-sample t-test in nQuery 8 (www.statsols.com). The number of 20 evaluable subjects in each sequence on moxifloxacin (40 over both Day 10 and 16) also agrees with recent recommendations of the FDA, which proposes at least 20 subjects ([Huang 2019](#)).

11.2. Analysis Populations

The following populations are defined for this study:

- **Safety Population:** all subjects who received at least one dose of study drug (SC setmelanotide, SC placebo, oral moxifloxacin, or oral placebo).
- **Pharmacokinetic Population:** all subjects who received at least 1 dose of setmelanotide or moxifloxacin and have at least one quantifiable concentration of setmelanotide or moxifloxacin. A subject may be excluded from the PK summary statistics and statistical analysis if the subject has an AE of vomiting that occurs at or before 2 times the median Tmax during moxifloxacin dosing.
- **QT/QTc Population:** all subjects in the Safety Population with measurements at baseline as well as on-treatment with at least one post-dose timepoint with a valid ΔQTcF value.

The QT/QTc population will be used for the by-timepoint and categorical analyses of the cardiodynamic ECG parameters.

- **PK/QTc Population:** all subjects who are in both the QT/QTc and PK populations with at least 1 pair of post-dose PK and QTcF data from the same timepoint as well as subjects in the QT/QTc population who received placebo. The PK/QTc population will be used for the C-QTc analysis. The PK/QTc population will be defined for setmelanotide and for moxifloxacin.

11.3. Planned Analysis

Separate statistical and PK analysis plans will be developed, which will include more technical and detailed descriptions of the statistical and PK analyses described in this section. This section is a summary of the planned statistical analyses of the most important endpoints, including primary and other endpoints.

11.3.1. Cardiodynamic ECG Assessment

The primary analysis will be based on C-QTc modeling of the relationship between plasma concentrations of setmelanotide (or placebo) and $\Delta QTcF$ (using Day -1 time-matched Holter ECGs as baseline) with the intent to exclude an effect of $\Delta\Delta QTcF > 10$ msec at clinically relevant plasma levels, using the concepts presented in the “Scientific White Paper on C-QTc modeling” (Garnett 2018b, Garnett 2018a). After development of the C-QTc model and assessment of model performance through nonparametric bootstrapping, the $\Delta\Delta QTcF$ associated with the Cmax of therapeutic and supratherapeutic doses will be computed using bias-corrected 90% CI. An increase in QTc of ≥ 10 msec can be ruled out if the upper 90% CI is < 10 msec.

The change from baseline (Δ) and placebo-corrected change from baseline ($\Delta\Delta$) QTcF, HR, PR, and QRS will be summarized by nominal time and treatment using descriptive statistics. An analysis of categorical outliers will be performed for changes in QTcF, HR, PR, and QRS, and T-wave morphology, and U-wave presence and results will be summarized.

